### **Appendix 3. List of Biologics for CD Treatment**

The drug names of biologics considered as CD treatment are listed below.

No.	Drug Class	Drug Name
1	TNF $\alpha$ antagonist	Adalimumab
2	TNF $\alpha$ antagonist	Certolizumab/Certolizumab Pegol
3	TNF $\alpha$ antagonist	Infliximab
4	TNF $\alpha$ antagonist	TNF $\alpha$ antagonist biosimilar (to adalimumab, Certolizumab/Certolizumab Pegol, or infliximab)
5	Integrin antagonist	Natalizumab
6	Integrin antagonist	Vedolizumab
7	Interleukin antagonist	Ustekinumab

CCI

CCI

CCI

CCI

CCI

## Appendix 5. Calculation of Standard Body Weight

The following table will be used to determine the standard body weight for each subject. Height from the eCRF will be used and is assumed to be measured without shoes.

Women			
Height in cm (in shoes)*	Standard Weight in kg	Height in cm (in shoes)*	Standard Weight in kg
127	41.2	163	60.2
128	41.7	164	60.7
129	42.3	165	61.3
130	42.8	166	61.9
131	43.3	167	62.4
132	43.8	168	62.9
133	44.4	169	63.4
134	44.9	170	63.9
135	45.4	171	64.5
136	45.9	172	65.0
137	46.4	173	65.5
138	47.0	174	66.0
139	47.5	175	66.6
140	48.0	176	67.2
141	48.6	177	67.7
142	49.1	178	68.3
143	49.6	179	68.8
144	50.2	180	69.3
145	50.7	181	69.8
146	51.2	182	70.3
147	51.8	183	70.8
148	52.3	184	71.3
149	52.8	185	71.8
150	53.1	186	72.3
151	54.1	187	72.8
152	54.5	188	73.3
153	55.0	189	73.8
154	55.4	190	74.3
155	55.9	191	74.9
156	56.4	192	75.4
157	57.0	193	76.0
158	57.5	194	76.5
159	58.1	195	77.0
160	58.6	196	77.6
161	59.1	197	78.1
162	59.6	198	78.6

\* add 2.0 cm if shoeless. Please round height to a whole number and select the appropriate standard weight (e.g., height 157.4 cm will be rounded to 157 cm; 157.5 cm will be rounded to 158 cm.)

Men			
Height in cm (in shoes)*	Standard Weight in kg	Height in cm (in shoes)*	Standard Weight in kg
142	54.4	179	71.9
143	54.9	180	72.4
144	55.4	181	73.0
145	55.8	182	73.6
146	56.3	183	74.3
147	56.8	184	74.8
148	57.2	185	75.5
149	57.7	186	76.2
150	58.2	187	76.9
151	58.6	188	77.6
152	59.1	189	78.2
153	59.6	190	78.8
154	60.0	191	79.6
155	60.5	192	80.4
156	61.0	193	81.2
157	61.4	194	82.1
158	61.9	195	82.9
159	62.2	196	83.8
160	62.6	197	84.7
161	62.9	198	85.4
162	63.3	199	86.1
163	63.7	200	86.7
164	64.1	201	87.4
165	64.6	202	88.0
166	65.0	203	88.8
167	65.5	204	89.4
168	66.0	205	90.1
169	66.6	206	90.7
170	67.1	207	91.4
171	67.6	208	92.1
172	68.1	209	92.7
173	68.7	210	93.4
174	69.2	211	94.1
175	69.7	212	94.8
176	70.3	213	95.5
177	70.8	214	96.1
178	71.3		

\* add 2.0 cm if shoeless. Please round height to a whole number and select the appropriate standard weight (e.g., height 157.4 cm will be rounded to 157 cm; 157.5 cm will be rounded to 158 cm.)

## Appendix 6. Simple Endoscopic Score for Crohn's Disease (SES-CD)

Variables	Score			
	0	1	2	3
Size of ulcers (cm)	None	Aphthous ulcers (diameter 0.1-0.5)	Large ulcers (diameter >0.5-2)	Very large ulcers (diameter > 2)
Ulcerated Surface (%)	None	< 10	10-30	> 30
Affected surface (%)	Unaffected segment	< 50	50-75	> 75
Presence of narrowings	None	Single, can be passed	Multiple, can be passed	Cannot be passed

Total SES-CD: sum of the values of the 4 variables for the 5 bowel segments. Values are given to each variable and for every examined bowel segment (eg, rectum, left colon, transverse colon, right colon, and ileum); Total SES-CD will not be calculated for Study GS-US-419-4016.

{Daperno 2004}

For Study GS-US-419-4016, the Proctitis SES-CD score (which includes an overall assessment of both rectum and anal canal) and Anal Canal Segmental SES-CD score will **only** score **size of ulcers** and **ulcerated surface**. The Proctitis SES-CD score will be used to provide an endoscopic measure of proctitis. **CCI**

CCI

CCI

A 10x3 grid of black and white blocks. The first two columns contain 10 rows of blocks, while the third column contains only 9 rows. The blocks in the first column are mostly horizontal rectangles, while the second column contains a central vertical stack of blocks. The third column has a single vertical block in the top row and a horizontal block in the bottom row.

CCI

## **Appendix 10. Study Treatment Failure Rules for Luminal Disease Activity Related Efficacy Endpoints**

Study treatment failure rules described in this appendix apply to treatment failure that occurs during the course of the study, and will be applied to all the following efficacy endpoints related to luminal disease activity:

- [REDACTED]
- [REDACTED]
- [REDACTED]

- Proportion of subjects achieving proctitis remission at Week 24, in subjects that had moderately to severely active proctitis at baseline

All related efficacy data will be censored (set to missing) after treatment failure criteria are met, regardless of the observed data. Subjects who do not have sufficient measurements after censoring to determine the dichotomized endpoint(s) will be considered non-responder for corresponding endpoint (s). Study treatment failure rules override other data handling rules.

Subjects who have any of the following events will be considered a study treatment failure after the earliest event through the end of the study, regardless of the actual efficacy data collected.

### **I. Potentially effective corticosteroid use**

Potentially effective corticosteroids, for the purpose of this SAP, are corticosteroids that may impact the disease under study. **Potentially effective corticosteroids** include the following corticosteroids when administered for the indication of CD:

- 1) Commencement of:

Any steroid administered intramuscularly (IM), intravenously (IV), orally (PO), or rectally (PR) at any dose for 7 or more continuous days

- This rule applies regardless if a change in drug, dose, or route (from IM to IV to PO or PR or vice versa) occurs within the seven continuous days; and it includes oral steroids with intended local actions (eg, budesonide)

- 2) Escalation of concomitant steroid dose above the baseline dose for 7 or more continuous days. The baseline steroid dose is defined as the dose at Day 1 of the study. Prednisone equivalent dose will be used to determine escalation of concomitant systemic steroid dose even if there is a change in drug or route. For steroids with predominant local effect (eg, budesonide or any rectally administered steroid), this rule will apply to scenarios where the post-baseline dose is above the baseline dose via the same drug and the same route for 7 or more continuous days.

Potentially effective steroid use only includes use of steroids administered via routes that are IM, PO, IV, or PR. The below steroids will **not** be considered potentially effective steroids regardless of indication for use:

- A) ocular steroids (ie, eye drops)
- B) topical steroids (eg, cutaneously applied solely to the skin, or topically applied to the nasal mucosa)
- C) inhaled steroids (eg, inhalational fluticasone for asthma)
- D) intra-articular steroids (steroids administered directly into a joint)
- E) neuraxial steroids (steroids administered into the epidural or spinal space)

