5.4.1. Allowed Concomitant Medication

The allowed concomitant medication(s) for CD must be maintained at a stable dose for the noted time without dose alteration or discontinuation. Subjects should not initiate new induction therapy prior to the screening visit. If a new therapy has been recently initiated, the full induction course should be completed prior to screening consideration.

The allowed medications for CD are as follows:

- Oral 5-ASA compounds provided the dose prescribed has been stable for at least 4 weeks prior to randomization; dose must be stable for the first 10 weeks after randomization
- Azathioprine, 6-MP, or MTX provided the dose prescribed has been stable for 4 weeks prior to randomization; dose must be stable for the first 10 weeks after randomization
- Oral corticosteroid therapy (prednisone prescribed at a stable dose of \leq 20 mg/day or budesonide prescribed at a stable dose of \leq 6 mg/day) provided the dose prescribed has been stable for 4 weeks prior to randomization; dose must be stable for the first 10 weeks after randomization.
- Antidiarrheals for chronic diarrhea are allowed throughout the study as necessary for control of chronic diarrhea; stable doses are encouraged.
- Occasional use of non-steroidal anti-inflammatory drugs (NSAIDs) for transient symptoms is permitted; daily use of aspirin up to 162.5 mg for the purpose of cardiovascular prophylaxis is permitted.
- Antibiotics for the treatment of perianal fistulizing CD (eg, metronidazole, ciprofloxacin) provided the dose prescribed has been stable for the 2 weeks prior to randomization. Dose must remain stable for the first 10 weeks after randomization. Subjects who are on cyclic therapy must continue their standard low-dose regimen without change for the first 10 weeks after randomization
- Vedolizumab therapy (300 mg IV) for the treatment of concurrent luminal disease activity provided the dose has been stable for 14 weeks prior to randomization; subjects must remain on vedolizumab for the duration of their participation in the study. Subjects on concurrent vedolizumab therapy must not be taking concurrent azathioprine or 6-MP or methotrexate.

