5.5. Corticosteroid Tapering

Starting at Week 10, subjects who are on concomitant steroids must begin tapering steroid therapy. The dose should be reduced at a rate starting at 2.5 mg per week up to 5 mg per week (or equivalent taper if not prednisone) until the subject is no longer on steroids. Subjects who are on budesonide should have their daily dose reduced by 3 mg every 3 weeks until they are completely off steroids. For subjects undergoing taper, steroids may be increased or restarted at doses up to and including their baseline dose if return of symptoms is apparent. These subjects will not be considered treatment failures. Subjects who need to restart or increase steroid treatment at a dose that exceeds their baseline dose of steroids (dose may not exceed 20 mg/day prednisone [or equivalent] or budesonide 6 mg/day) will be considered treatment failures for all clinical endpoints but will be permitted to remain in the study and continue to receive study drug.

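### As worded, SAP Appendix 10 I(1) fails a post-taper steroid restart at or below the Day 1 dose, which Protocol 5.5 says is not a treatment failure; the visible effect is on proctitis remission

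*SAP*

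**What the plan says.** **Protocol 5.5.** "Starting at Week 10, subjects who are on concomitant steroids must begin tapering steroid therapy". For prednisone: "The dose should be reduced at a rate starting at 2.5 mg per week up to 5 mg per week"; for budesonide: "Subjects who are on budesonide should have their daily dose reduced by 3 mg every 3 weeks until they are completely off steroids". During the taper "steroids may be increased or restarted at doses up to and including their baseline dose if return of symptoms is apparent", and "These subjects will not be considered treatment failures". Only a dose above baseline makes the subject a failure, for all clinical endpoints.

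**SAP Appendix 10, part I.** There are two steroid triggers, both limited to use for Crohn's disease:

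- I(1), commencement: "Any steroid administered intramuscularly (IM), intravenously (IV), orally (PO), or rectally (PR) at any dose for 7 or more continuous days".
- I(2), escalation: a concomitant dose above the Day 1 dose for 7 or more continuous days.

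Only I(2) refers to the Day 1 dose. Once a trigger is met, "All related efficacy data will be censored (set to missing) after treatment failure criteria are met, regardless of the observed data". The appendix also gives the failure rules precedence over other data handling. A missing Week 24 proctitis score is not imputed, and the subject counts as a non-responder (SAP 6.3.2).

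**Reach.** Proctitis remission at Week 24 is the one unredacted endpoint listed in Appendix 10. Appendix 11 covers combined fistula response (primary), combined fistula remission and both time-to-event endpoints. Its triggers are antibiotics, immunomodulators and biologics; it has no steroid rule.

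**The concern.** The two documents classify the same permitted event in opposite ways. A restart, as distinct from an increase, presupposes that the subject had stopped, so the protocol's protection extends to subjects who reached zero. A subject at zero has no concomitant dose left to escalate, so on the SAP's wording a restart of 7 or more days falls under I(1) whatever the dose.

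At stake is a subject with baseline proctitis who follows the protocol, restarts at or below the Day 1 dose, and has a centrally read proctitis score of 0 at Week 24. Coded as written, the SAP discards that score and records a non-responder. Two programmers could also reasonably code the rule differently.

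**Working it through.** There is no stated figure to reproduce. The check has three parts: what each rule does with the same case, whether the case can arise before the endpoint is measured, and how much one such case would matter.

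**1. The rules applied to the same restarts.** Assume a Day 1 dose of 15 mg/day prednisone and a completed taper. The narrower reading confines I(1) to subjects not on steroids at Day 1.

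| Restart | SAP as worded | SAP, narrower reading | Protocol 5.5 |
|---|---|---|---|
| 10 mg for 5 days | not failed | not failed | not failed |
| 10 mg for 7 days | **failed** | not failed | not failed |
| 15 mg for 14 days | **failed** | not failed | not failed |
| 20 mg for 14 days | failed | failed | failed |

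The conflict is confined to the middle rows: at or below the Day 1 dose, for 7 days or more. The wording also gives an odd ordering. With a Day 1 dose of 20 mg, going from 2.5 mg back to 20 mg is not a failure under I(2), while going from 0 to 2.5 mg for 7 days is a failure under I(1).

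**2. Can it happen before Week 24?** Inputs: maximum Day 1 doses of 20 mg/day prednisone and 6 mg/day budesonide (Protocol 5.4.1); the taper rates above; sigmoidoscopy up to 14 days before the Week 24 visit (Protocol 6.5). Nominal weeks are used and visit windows ignored.

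- Prednisone 20 mg at 2.5 mg/week: 20 / 2.5 = 8 steps, so off at Week 17 (first cut at Week 10) or Week 18 (first cut a week later).
- Prednisone 20 mg at 5 mg/week: 20 / 5 = 4 steps, so off at Week 13 or 14.
- Budesonide 6 mg: 6 / 3 = 2 steps, so off at Week 13 (first cut at Week 10) or Week 16 (first cut at Week 13).

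Take the trigger as met once 7 days are complete. The latest start that fails the subject before the sigmoidoscopy is then one week earlier: Week 22 − 1 = 21, or Week 24 − 1 = 23. With the later off-date in each case:

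| Taper | Off at | Window for a failing restart |
|---|---|---|
| Prednisone 20 mg, 2.5 mg/week | Week 18 | 21 − 18 = 3 to 23 − 18 = 5 weeks |
| Prednisone 20 mg, 5 mg/week | Week 14 | 21 − 14 = 7 to 23 − 14 = 9 weeks |
| Budesonide 6 mg | Week 16 | 21 − 16 = 5 to 23 − 16 = 7 weeks |

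So the case can arise, even in the slowest taper.

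**3. Weight of one case.** The planned arms are 30, 30 and 15, and the endpoint uses only subjects with moderately to severely active proctitis at baseline. That number is not given. Assuming n = 5 to 15 such subjects in an arm, one reclassified remitter moves the arm's rate by 100 / n, that is 100 / 5 = 20 to 100 / 15 = 6.7 percentage points. This is the effect of one case if it occurs; it does not show that a case is likely.

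**The case against.** The best counter-argument is that commencement is undefined and I(1) may be meant only for subjects not on steroids at Day 1, with I(2) governing the rest. I(2) gives this some support: it compares prednisone-equivalent doses even when the drug or route changes, which would do little if any newly started systemic steroid lasting 7 days were already caught by I(1). On that reading the conflict and the odd ordering both vanish. The reading is available, so an intended contradiction is not proven. But the SAP does not state it, and the immunomodulator rule in the same appendix does carry an explicit exemption for classes already taken on Day 1. The steroid rule has none.

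Two further points stand in part. Protocol 5.5 speaks of failure for clinical endpoints and does not say whether a centrally read endoscopic score is one, so the clash with proctitis remission is less direct than with a symptom endpoint. And scoring resumed steroid use as failure is a recognised conservative choice; if intended, it needs to be documented. No visible text does so, although parts of SAP Section 6 are redacted.

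A reader might also infer a direction of bias: an arm in which more subjects come off steroids has more of them exposed to I(1). The documents do not support this. The taper is mandatory in every arm, and an arm with better disease control could have more completed tapers but fewer symptomatic restarts.

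**Conclusion.** The discrepancy is real as a matter of wording. Applied as written, Appendix 10 I(1) scores a protocol-permitted restart of 7 or more days, at or below the Day 1 dose and for Crohn's disease, as non-response for proctitis remission. This rests on the literal reading of an undefined term.

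The consequence is limited. It visibly touches one secondary endpoint in a subset, in a descriptive study without hypothesis testing; the effect on the redacted Appendix 10 endpoints cannot be judged. It would be wrong to infer that the primary endpoint or the other fistula endpoints are affected, since Appendix 11 has no steroid rule.

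The number affected cannot be computed. A subject must have both a steroid and proctitis at baseline, stay on treatment past Week 10, complete the taper, relapse symptomatically, restart for at least 7 days and still score 0. The documents give no rate for any of these. It would also be an overstatement to say that every taper leaves six weeks or more of exposure: after the 7-day minimum and the sigmoidoscopy allowance, the slowest prednisone taper from 20 mg leaves about 3 to 5.

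**What to change.** Before unblinding, reconcile Appendix 10 I(1) with Protocol 5.5:

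- State that, for subjects on a steroid for Crohn's disease at Day 1, a post-taper restart at or below the Day 1 dose is not commencement and is assessed only under the above-baseline rule in I(2).
- State that a steroid with predominantly local effect not in use at Day 1 (a new drug or route) still falls under I(1). Otherwise a Day 1 prednisone user who newly starts budesonide or a rectal steroid might be caught by neither trigger, because I(2) compares local steroids only within the same drug and route.
- If the stricter rule is intended, record it as a departure from the protocol and report proctitis remission under both definitions.

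The cost is a sentence or two of SAP text and one programming condition, using the Day 1 dose that I(2) already requires. The last option adds one further summary. Only the analysis definition changes; patient care does not.

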## **II. Potentially effective immunomodulator use**

### **Commencement of a different class of oral, IM, SC, or IV immunomodulator drugs**

(where the subject was not previously taking concomitant immunomodulators of the same class on Day 1), including but not limited to 6-MP, azathioprine, MTX, 6-thioguanine, and prohibited immunomodulators including but not limited to cyclosporine, leflunomide, tacrolimus, thalidomide regardless of dose, for 7 continuous days. The use of an immunomodulator will be considered potentially effective when it is administered for the indication of CD.

## **III. Potentially effective biologic agent use**

**Commencement of a biologic agent** including but not limited to TNF $\alpha$  antagonists, IL-12/23 antagonists, and vedolizumab (or similar agents), regardless of indication for use and duration ([Appendix 3](#)).

## **Appendix 11. Study Treatment Failure Rules for Perianal Fistulizing CD Activity Related Efficacy Endpoints**

Study treatment failure rules described in this appendix apply to treatment failure that occurs during the course of the study, and will be applied to all the following efficacy endpoints related to perianal fistulizing CD activity:

- Proportion of subjects establishing combined fistula response at Week 24
- Proportion of subjects establishing combined fistula remission at Week 24
- Time to clinical fistula response
- Time to clinical fistula remission

All related efficacy data will be censored (set to missing) after treatment failure criteria are met, regardless of the observed data. Subjects who do not have sufficient measurements after censoring to determine the dichotomized endpoint(s) will be considered non-responder for corresponding endpoint (s). Study treatment failure rules override other data handling rules.

Subjects who have any of the following events will be considered a study treatment failure after the earliest event through the end of the study, regardless of the actual efficacy data collected.

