Residual inflammation of the fistula tract may be responsible for the occurrence of *de novo* perianal abscesses and for fistula recurrence in patients treated for fistulizing CD. The undetected pelvic abscess may become clinically apparent only after cessation of drainage from external orifices, and becomes a source of continuous inflammatory reaction. Given these challenges in assessing the activity and complications of the perianal CD, it may be warranted to combine MRI assessment with clinical examination to evaluate the efficacy of study treatment. A 2 cm cutoff for fluid collection as entry criteria was chosen as it represents the clinical threshold which warrants drainage. A cutoff of \leq 1 cm for fluid collection was chosen as part of the combined primary endpoint to ensure a more stringent definition of response to treatment was used that is differentiated from the clinical threshold for drainage.

In conclusion, this study will use MRI to evaluate healing of fistulae in addition to clinical assessment of drainage and fistula closure. MRI images will be centrally read in a blinded manner. These measures will provide a comprehensive and objective assessment of disease activity and treatment response in fistulizing CD.

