3.5. Criteria for Study Drug Interruption or Discontinuation

3.5.1. Study Drug Interruption Considerations

The Study Medical Monitor should be consulted prior to study drug interruption when medically feasible.

Study drug interruption should be considered in the following circumstances (*prior to resumption of study drug, the investigator should discuss the case with the Study Medical Monitor*):

- Intercurrent illness that would, in the judgment of the investigator, affect assessments of clinical status to a significant degree
- Subject is scheduled for elective or emergency surgery (excluding minor skin procedures under local or no anesthesia); timing of study drug interruption should be determined in consultation with the Study Medical Monitor
- Any subject who develops a new infection during the study should undergo prompt and complete diagnostic testing appropriate for an immunocompromised individual, and the subject should be closely monitored

NOTE: During the time of study drug interruption for any of the above, the subject may continue to have study visits and to take part in procedures and assessments, if deemed medically appropriate by the investigator.

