3.8. Luminal Disease Activity - Disease Worsening Criteria

Subjects meeting the following disease worsening criterion after Week 10 must be discontinued from blinded treatment and will be offered the option to receive open-label filgotinib by entering into the separate LTE study:

- An increase in CDAI of ≥ 100 points from the Week 10 value with CDAI ≥ 220 at 2 consecutive visits

Determination of disease worsening may be made at scheduled or unscheduled visits (eg, a study visit followed by an unscheduled visit, or 2 sequential unscheduled visits anytime subsequent to the Week 10 visit).

- All subjects meeting disease worsening criteria should undergo a pelvic MRI and flexible sigmoidoscopy prior to exiting the study (Refer to Sections 6.5 and 6.6 for details regarding the flexible sigmoidoscopy and MRI).
- If a subject experiences significant worsening of underlying CD, which requires any of the prohibited medications (refer to Section 5.4.2), or surgical intervention at any point during the study, treatment discontinuation should be considered at investigator's discretion, in consultation with medical monitor if feasible (refer to Section 3.5.2); these subjects do not qualify for LTE study.

[figure not shown]

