### **I. Potentially effective antibiotics use**

Potentially effective antibiotics, for the purpose of this SAP, include metronidazole and ciprofloxacin, which may impact the subject's perianal fistulizing CD when administered as following for the indication of perianal fistulizing CD or CD:

- Commencement of a new antibiotics use after the first dosing date of study drug for 7 or more days;
- Escalation of the dose of antibiotics above the baseline dose for 7 or more days.

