## **II. Potentially effective immunomodulator use**

### **Commencement of a different class of oral, IM, SC, or IV immunomodulator drugs**

(where the subject was not previously taking concomitant immunomodulators of the same class on Day 1), including but not limited to 6-MP, azathioprine, MTX, 6-thioguanine, and prohibited immunomodulators including but not limited to cyclosporine, leflunomide, tacrolimus, thalidomide regardless of dose, for 7 continuous days. The use of an immunomodulator will be considered potentially effective when it is administered for the indication of perianal fistulizing CD or CD.

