## **III. Potentially effective biologic agent use**

**Commencement of a biologic agent** including TNF $\alpha$  antagonists, regardless of indication for use and duration ([Appendix 2](#)).

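### SAP Appendix 11 has no failure rule for perianal procedures after first dose, so a Week 24 result produced by a procedure can be scored as a fistula response

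*SAP*

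**What the plan says.** SAP Section 6.1 sends the reader to Appendices 10 and 11 for the definition of study treatment failure. Appendix 11 covers "Proportion of subjects establishing combined fistula response at Week 24", combined remission at Week 24, and the times to clinical fistula response and remission. Efficacy data after a failure event are set to missing, and the failure rules take precedence over other data handling rules.

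The governing sentence is "Subjects who have any of the following events will be considered a study treatment failure after the earliest event". The events are listed under three items:

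- **I, antibiotics.** Metronidazole or ciprofloxacin given for perianal fistulizing CD or CD: "Commencement of a new antibiotics use after the first dosing date of study drug for 7 or more days", or a dose raised above baseline for as long.
- **II, immunomodulators.** "Commencement of a different class of oral, IM, SC, or IV immunomodulator drugs".
- **III, biologics.** A biologic agent started, "regardless of indication for use and duration".

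Appendix 12 follows directly, and no redaction is visible within Appendix 11. Appendix 10, which covers the luminal endpoints, also lists drugs only.

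The protocol deals with surgery in two places. Section 3.5.1 lists "Subject is scheduled for elective or emergency surgery" among the reasons to consider interrupting study drug, and lets visits and assessments continue meanwhile. Section 3.8 addresses significant worsening of CD that needs a prohibited medication or "surgical intervention at any point during the study, treatment discontinuation should be considered", at the investigator's discretion. Neither section makes the subject a non-responder.

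**The concern.** The primary objective is the effect of filgotinib on combined fistula response. A new antibiotic, immunomodulator or biologic is treated as failure because it could produce the outcome in place of study drug. A perianal procedure can do the same, and Protocol Section 3.8 names surgery and prohibited medication together as consequences of worsening. The SAP carried only the drug half into its failure rules.

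The protocol is careful about procedures before baseline: setons must be out at least 14 days before randomization (inclusion criterion 7), and an abscess that would otherwise exclude must have been drained and treated at least 4 weeks before Day 1 (exclusion criterion 11). No visible analysis rule does this after baseline. At stake is whether the Week 24 rates, and the times to closure, describe the drug or the drug plus a procedure.

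**Working it through.** **1. The plan's own figure.** The 90% Clopper-Pearson limits for x responders of n are the 0.05 quantile of Beta(x, n − x + 1) and the 0.95 quantile of Beta(x + 1, n − x). For 15/30 this gives 33.9% to 66.1%, printed as 34% to 66% (SAP Table 1-1, Protocol Table 8-1). All seven rows reproduce. The table is not in dispute.

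**2. One subject followed through the rules.** Take a subject who has a perianal procedure after Week 10 for a non-serious event.

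- *Mandatory exits.* Protocol Section 3.5.2 requires stopping for serious infection. The perianal non-response exit (Section 3.7) depends on PDAI subscores at Weeks 6 and 10. The later worsening exit (Section 3.8) uses CDAI only. None need apply.
- *Failure rules.* Unless a listed drug is also started or escalated as Appendix 11 describes, no item is met.
- *Non-responder imputation.* SAP Section 6.1 applies it when measurements are insufficient. Here they are complete.
- *Scoring.* Closure is observed absence of drainage under gentle compression; the MRI component is absence of a collection over 1 cm. Neither definition asks what caused the result.

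The subject is scored as observed. For the two time-to-event endpoints, closure first seen after the procedure, at a scheduled or unscheduled visit, counts as the event (SAP Table 6-1).

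**3. Size per subject.** Planned arms are 30, 30 and 15. One reclassified subject moves placebo by 1/15 = 6.7 points or a filgotinib arm by 1/30 = 3.3 points.

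**4. Illustration (all counts assumed).** Suppose scoring as written gives 15/30 on one filgotinib dose and 5/15 on placebo. With f filgotinib and p placebo responders rescored as failures, the difference is (15 − f)/30 − (5 − p)/15. The SAP names no interval method for the difference; Newcombe is used here.

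| f | p | Rates | Difference, points (90% CI) |
|---|---|---|---|
| 0 | 0 | 15/30 v 5/15 | 16.7 (−8.9 to 38.2) |
| 0 | 1 | 15/30 v 4/15 | 23.3 (−2.3 to 43.5) |
| 0 | 2 | 15/30 v 3/15 | 30.0 (4.6 to 48.5) |
| 1 | 1 | 14/30 v 4/15 | 20.0 (−5.5 to 40.3) |
| 2 | 0 | 13/30 v 5/15 | 10.0 (−15.2 to 31.8) |

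The correction can raise or lower the estimate, depending on which arm has the procedures.

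**5. Chance of at least one procedure in an arm.** The documents give no procedure rate, so q is assumed over a range; the chance is 1 − (1 − q)^n.

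| q | Placebo, n = 15 | One filgotinib arm, n = 30 |
|---|---|---|
| 3% | 37% | 60% |
| 5% | 54% | 79% |
| 10% | 79% | 96% |
| 20% | 96% | over 99% |

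These are chances of a procedure, not of a misclassified responder. Only some of these subjects would reach Week 24, avoid rule I and meet both components.

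**The case against.** Several safeguards narrow the gap. Exclusion criteria 11 and 15 keep out subjects with an abscess over 2 cm or one needing drainage (unless already drained and treated), and those likely to need surgery during the study. Rule I catches a procedure accompanied by 7 or more days of new or escalated metronidazole or ciprofloxacin for perianal CD or CD. Week 10 non-responders must stop blinded treatment. A subject who leaves without sufficient Week 24 data is a non-responder. All of this stands, and it lowers the frequency. It does not settle how to score a subject who has a procedure, takes another antibiotic or a shorter course, and attends Week 24.

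A reader might infer that draining an abscess alone makes a responder. The documents do not support that: response also needs at least one fewer draining opening among those present at baseline, and drainage of a collection acts on the MRI component. Protocol Section 1.3 notes that an abscess may become apparent only after external drainage has stopped, so the clinical component may already have been met.

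A reader might also take the sentence "A 2 cm cutoff for fluid collection as entry criteria was chosen as it represents the clinical threshold which warrants drainage" as a forecast of in-study drainage. It explains an entry cutoff. Likewise, Section 3.5.1 is not specific to perianal surgery, and Section 3.8 is conditional on worsening.

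Unseen text limits confidence. Reasons 3 and 4 in the SAP Section 6.1 list, and text after the imputation paragraph, are redacted. Protocol Section 6.7 defers details of the perianal assessment to a manual that is not available here. A rule for treated openings could sit in either place, although Section 6.1 points to the appendices for the failure definition.

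Finally, the trial is descriptive, without hypothesis tests. That lowers the severity, but the point estimates are then the main product.

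**Conclusion.** The gap is real, should be fixed, and is held with moderate confidence. As written, a subject with a perianal procedure after first dose who does not meet rule I and has Week 24 data is scored on what is observed, whatever produced it. The firm figures are 6.7 points per placebo subject and 3.3 points per filgotinib subject, at the planned arm sizes and only where the procedure made the difference between non-response and response.

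Two stronger conclusions are tempting. One is that the gap dilutes the filgotinib effect, because surgery follows worse disease. The documents give no procedure rates, and Protocol Section 1.5 reports more infections on active treatment, so the direction is unknown. The other is that the difference could fall by more than half. Suppose the true counts were 15/30 and 3/15, a difference of 30 points. With three placebo and one filgotinib subject added as responders, 16/30 − 6/15 gives 13.3 points. That needs 3 of 15 placebo subjects each to have a procedure, stay in, avoid rule I and meet both components only because of the procedure. Nothing in the documents supports such counts.

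**What to change.** Add an item IV to SAP Appendix 11: *perianal surgical or procedural intervention for fistula or abscess after first dose of study drug*. Then state four things.

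1. **Binary endpoints.** These subjects are non-responders for combined response and combined remission. The Week 24 carry-forward of drainage counts and the baseline-MRI imputation in SAP Section 6.2.2 do not apply to them. The existing override clause implies this, but it should be explicit.
2. **Time-to-event endpoints.** Closure first seen after the procedure is not an event. Treat the subject as not achieving it, for example by censoring at the end of planned follow-up or by taking the procedure as a competing event. Setting later data to missing would censor near the procedure, which is informative because it assumes that operated subjects had the same prospects as the rest.
3. **Data source.** Protocol Section 7.1.1 does not count procedures as AEs, and a stable pre-existing condition is not one either. A procedure on an unchanged baseline fistula could therefore leave no AE record. Identify procedures, with type and date, from AE, concomitant-medication and site source records before unblinding.
4. **Reporting.** Give procedure counts by arm and a sensitivity analysis that uses the observed data.

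The cost is a short SAP addition, some blinded data review, and possibly slightly lower response rates. If the SAP is already final, SAP Section 1 allows the change to be documented in the CSR. Only the analysis changes; patient care does not.
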